5.3 Treatment of patients

Table 5–1 List of products provided by Novo Nordisk

Compound Name	Strength	Dosage form	Route of administration	Treatment period
Concizumab B²,	100 mg/mL	3 mL solution in a 3 mL cartridge ³ .	S.c. administration using NovoPen [®] 4	For prophylactic treatment for at least 76 weeks.
Turoctocog alfa (NovoEight[®])⁴, Sodium chloride solution 4ml	2000 IU/vial	Powder for solution for injection Solvent for solution for i.v. injection used for reconstitution of turoctocog alfa.	I.v. administration	For treatment of breakthrough bleeding episodes (or prophylaxis in the screening and follow-up phases), at the discretion of the treating physician (patients may choose to use other familiar pre-trial non-modified FVIII drug). For further information see section 5.3.2

Concizumab will be given s.c., once daily for a total dosing period of at least 76 weeks.

The NovoPen[®]4 injector will be supplied by Novo Nordisk and used for the s.c. administration of concizumab. It will be labelled in accordance with national legislation and a copy of the label can be found within the Trial Materials Manual, see Section [9.1](#).

The first dose of concizumab will be given at the trial site under medical supervision. After the initial dose the patient must be observed for potential emergence of AEs/safety signals for at least 2 hours at the trial site. At the screening visit and the first scheduled treatment visit patients will be trained in s.c. administration of concizumab with NovoPen[®] 4 and in the use of eDiary.

Investigational medicinal product (IMP)

³ Not to be confused with the daily injected volume (~150 µL, depending on dose strength and body weight)

⁴ Non-investigational medicinal product (NIMP)

Protocol
 Trial ID:NN7415-4255
 UTN:U1111-1179-3872
 EudraCT no.:2016-000614-29

~~CONFIDENTIAL~~

Date:	28 August 2018	Novo Nordisk
Version:	5.0	
Status:	Final	
Page:	34 of 127	

In case safety concerns meet the criteria (See section [12](#)) for putting enrolment of additional patients on hold, further enrolment in the trial will be halted. Dosing of patients on treatment may continue while further evaluation is made by the safety committee. In case of other safety concerns all available data will be evaluated by the DMC see Section [12.8.2](#).

5.3.1 Dose escalation

Bleeding episodes will be assessed during the trial both at scheduled visits and also between visits. The first 2 weeks of the treatment with concizumab 0.15 mg/kg is considered as a run-in period. Hence the bleeding episodes occurring during the first 2 weeks should not influence a dose escalation decision.

All spontaneous bleeding episodes (sBEs) are counted from 2 weeks after visit 2 (first-dose visit) until visit 16 (end-of-treatment visit), i.e. a total of up to 124 weeks. Dose-escalation will be based on the number of spontaneous, treated bleeding episodes in patients within preceding 12 weeks. However, before dose-escalation can occur, to ensure the safety of the patients, the investigator must take into account the full clinical picture the patient is presenting with and all available laboratory results, including coagulation parameters.

Dose 0.15 mg/kg:

When a sBE occurs, the investigator will determine if ≥ 3 sBEs have occurred within the preceding 12 weeks since visit 2+2weeks (including the current sBE). If yes, and if investigator deems it safe, the patient will have to be dose escalated from 0.15 to 0.20 mg/kg at the next scheduled visit. If the investigator judges that this visit is scheduled too late, he/she should contact the patient for an unscheduled visit.

Dose 0.20 mg/kg:

When an sBE occurs, the investigator will determine if ≥ 3 sBEs have occurred within the preceding 12 weeks (including the current sBE), counting only new sBEs from the beginning of the 0.20 mg/kg treatment period. If yes, and if investigator deems it safe, the patient will have to be dose escalated from 0.20 to 0.25 mg/kg at the next scheduled visit. If the investigator judges that this visit is scheduled too late, he/she should contact the patient for an unscheduled visit.

Dose 0.25 mg/kg:

Patients are not dose escalated further regardless of the number of sBEs. When an sBE occurs, the investigator will determine if ≥ 3 sBEs have occurred within the preceding 12 weeks (including the current sBE), counting only the new sBEs from the beginning of the 0,25mg/kg treatment period. If yes, then the patient must be discontinued from treatment due to lack of efficacy, see Section [6.4](#).

Since the patient may have to wait up to 8 weeks for the next scheduled visit (in the extension part), the possibility of dose escalation at unscheduled visits is necessary for the dose-escalation eliciting bleeding episode to occur soon after previous scheduled visit.

Protocol
 Trial ID:NN7415-4255
 UTN:U1111-1179-3872
 EudraCT no.:2016-000614-29

CONFIDENTIAL

Date:
 Version:
 Status:
 Page:

28 August 2018
 5.0
 Final
 35 of 127

Novo Nordisk

[figure not shown]

Figure 5–3 Dose escalation of concizumab for one individual patient

5.3.2 Treatment of bleeding episodes during the trial

Bleeding episodes (main part, extension part, and follow-up part) :

Breakthrough bleeding episodes during the course of the trial will be treated at the discretion of the treating physician, with either turoctocog alfa/Novoeight[®] (rFVIII) (provided by Novo Nordisk) or other non-modified FVIII products (not provided by Novo Nordisk) . Treatment dose is chosen at the discretion of the investigator; however; in this trial any given single dose should not exceed 50 IU/kg (Table 8-4) . The patient can treat himself and then he must call the site. The bleeding episodes must be recorded in the eDiary. Bleeding episodes must be recorded in the electronic case report form (eCRF) as an AE/SAE if fatal, life threatening or evaluated as related to trial product (see section [12.1](#))

FVIII prophylactic treatment (follow-up part) :

During the follow-up part of the trial (i.e. from concizumab end-of-treatment visit to end-of-trial visit) patients will receive pre -trial FVIII medication at the discretion of the treating investigator, who will also choose dose levels. Only turoctocog alfa/NovoEight[®] will be provided by Novo Nordisk for this purpose.

5.3.3 Prohibited medication

- Treatment with anti-fibrinolytics (e.g. tranexamic acid, aminocaproic acid)*
- Heparin, except for sealing of central venous access ports according to local practice
- Vitamin-K antagonists
- Direct oral anti-coagulants (DOACs)
- Modified FVIII products with extended half-life

Protocol
 Trial ID:NN7415-4255
 UTN:U1111-1179-3872
 EudraCT no.:2016-000614-29

~~CONFIDENTIAL~~

Date: 28 August 2018
 Version: 5.0
 Status: Final
 Page: 36 of 127

Novo Nordisk

*Local/topical use is allowed. Use of single systemic doses in severe bleeding episodes, after careful benefit-risk evaluation, is allowed. Not applicable for France.

5.4 Treatment after discontinuation of trial product

When discontinuing trial products the patient should be switched to a suitable marketed product at the discretion of the investigator. The patient will not be provided with concizumab or FVIII (turoctocog alfa/NovoEight[®]) by Novo Nordisk after end of trial (visit 17).

5.5 Rationale for treatment

Concizumab is a monoclonal antibody and as such offers the possibility of s.c. administration. S.c. administration of an effective prophylactic drug has potential to reduce treatment burden significantly compared to the currently approved prophylactic drugs which have to be administered i.v.

The treatment period of at least 24 weeks (the main part of the trial) is considered necessary for providing data that allow demonstration of CPoC and to support decision-making regarding a phase 3 confirmatory trial. Dosing for up to an additional 102 weeks will provide valuable long-term efficacy and safety.

Breakthrough bleeding episodes may occur during prophylactic regimens with conventional FVIII replacement therapy. Therefore, it is expected that breakthrough bleeding episodes will also occur during prophylaxis with concizumab even if clinical proof of concept is demonstrated. Consequently turoctocog alfa (FVIII) will be provided by Novo Nordisk A/S in this trial for treatment of breakthrough bleeding episodes.

Patients are not obliged to use turoctocog alfa (FVIII) and can use their previously used FVIII concentrate for treatment of breakthrough bleeding episode. Novo Nordisk A/S will not provide or reimburse these products.

Please refer to the Investigator's Brochure for further information.

Protocol
Trial ID:NN7415-4255
UTN:U1111-1179-3872
EudraCT no.:2016-000614-29

~~CONFIDENTIAL~~

Date: 28 August 2018
Version: 5.0
Status: Final
Page: 37 of 127

Novo Nordisk

6 Trial population

6.1 Number of patients

Number of patients planned to be screened: 36

Number of patients planned to be started on trial product(s): 33

Number of patients planned to complete the trial: 30

Discontinued patients will not be replaced.

6.2 Inclusion criteria

For an eligible patient, all inclusion criteria must be answered “yes”.

1. Informed consent obtained before any trial-related activities. Trial-related activities are any procedures that are carried out as part of the trial, including activities to determine suitability for the trial.
2. Male patients aged ≥ 18 years at the time of signing informed consent, diagnosed with severe haemophilia A (FVIII activity $<1\%$), based on medical records or results at screening.
3. For patients being treated on-demand with FVIII replacement therapy, a minimum of six documented and treated bleeding episodes during the 24 weeks (or twelve bleeds during 52 weeks) prior to screening.

6.3 Exclusion criteria

For an eligible patient, all exclusion criteria must be answered “no”.

1. Known or suspected hypersensitivity to trial product(s) or related products.
2. Previous participation in this trial. Participation is defined as signed informed consent.
3. Participation in any clinical trial of an approved or non-approved investigational medicinal product within the last 30 days or 5 half-lives (whichever is longer) from the last drug administration before screening.
4. Any disorder, which in the investigator’s opinion might jeopardise patient’s safety or compliance with the protocol.
5. Known inherited or acquired bleeding disorder other than haemophilia A.
6. Major surgery conducted within one month prior to the initiation of trial activities or major surgery planned to occur during the trial.
7. Previous history of thromboembolic disease. Current clinical signs of thromboembolic disease, or patients who in the judgement of the investigator are considered at high risk of thromboembolic events.

Protocol
 Trial ID: NN7415-4255
 UTN: U1111-1179-3872
 EudraCT no.: 2016-000614-29

~~CONFIDENTIAL~~

Date: 28 August 2018
 Version: 5.0
 Status: Final
 Page: 38 of 127

Novo Nordisk

8. Mental incapacity, unwillingness to cooperate or language barrier precluding adequate understanding and cooperation.
9. Patients who, at screening, have a significant infection or known systemic inflammatory condition which require systemic treatment according to the investigator's judgement.
10. Hepatic dysfunction defined as elevated liver transaminases (ALT) >3 times the upper limit of normal laboratory reference ranges at screening.
11. Renal impairment defined as estimated glomerular filtration rate (eGFR) ≤ 60 mL/min/1.73m² based on serum creatinine measured at screening or evidence of renal damage.
12. Platelet count $\leq 100 \times 10^9$ /L at screening.
13. Fibrinogen level < the lower limit of normal at screening
14. Presence of inhibitors (neutralising antibodies) to Factor VIII (≥ 0.6 Bethesda Units) at screening measured by the Nijmegen method.
15. History of inhibitors towards FVIII based on investigator's knowledge or documentation in available medical records.

6.4 Criteria for premature discontinuation of trial product

The patient may be prematurely discontinued from trial product at the discretion of the investigator due to a safety concern.

The patient must be prematurely discontinued from trial product if the following applies:

1. Included in the trial in violation of the inclusion and/or exclusion criteria
2. Simultaneous participation in another clinical trial of an approved or non-approved investigational medicinal product.
3. Incapacity or unwillingness to follow the trial procedures
4. Anaphylactic reaction
5. Thromboembolic event
6. Event of disseminated intravascular coagulation (DIC)
7. Development of inhibitors to Factor VIII (≥ 0.6 BU)
8. Lack of efficacy due to neutralising antibodies towards concizumab
9. Lack of efficacy defined as ≥ 3 treated sBEs within the previous 12 weeks in patients being treated with the highest dose level (0.25 mg/kg) of concizumab.

See Section [8.1.4](#) for procedures to be performed for patients discontinuing trial product prematurely.

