o	The trial patient must be in a non-bleeding state at the time of the first trial product administration (TPA), and should not have received any haemostatic drug (e.g. FVIII) for prophylaxis or treatment of a bleeding episode within a period of 48 hours prior to first TPA.
p	Patient should be dose escalated at next scheduled visit if he experiences ≥ 3 spontaneous bleeding episodes within the preceding 12 weeks of treatment with concizumab. If investigator judges that next scheduled visit is too late an unscheduled visit should be performed for dose escalation.
q	Home treatment training must take place at visit 2 at the latest and whenever needed afterwards. Home treatment training comprises handing out of Direction for Use (DFU), training in administration of concizumab with NovoPen [®] 4, turoctocog alfa and data entry in eDiary. Further the patients will be trained in recognition of signs/symptoms of thrombosis.
r	In case patients are participating in the 24 hour PK-session the sampling time points for thrombin generation, concizumab ELISA and Free TFPI are: pre-dose (-1 hour), 1h (\pm 10 min), 3h (\pm 10 min), 6h (\pm 10 min), 9h (\pm 10 min), 12h (\pm 20 min) and 24h (\pm 20 min). All time points, except pre-dose, occur after concizumab administration
s	Visit repeated every 8 week until patient either discontinues, completes extension or is enrolled into a subsequent trial with concizumab
t	For patients continuing a subsequent trial End of Trial must be completed at visit 16. For patients declining participation in a subsequent trial the End of Trial must be completed at visit 17, 8 weeks after End of Treatment.
u	PRO questionnaires should only be completed at 15.1 for patients continuing in the prolongation of the trial.
v	PRO questionnaires should only be completed at visit 16 for patients not continuing in the prolongation of the trial

Protocol
 Trial ID:NN7415-4255
 UTN:U1111-1179-3872
 EudraCT no.:2016-000614-29

~~CONFIDENTIAL~~

Date:	28 August 2018	Novo Nordisk
Version:	5.0	
Status:	Final	
Page:	21 of 127	

3 Background information and rationale for the trial

The trial will be conducted in compliance with this protocol, International Conference on Harmonisation Good Clinical Practice (ICH GCP)¹ and applicable regulatory requirements, and in accordance with the Declaration of Helsinki² and ISO 14155³.

In this document, the term investigator refers to the individual responsible for the overall conduct of the clinical trial at a trial site.

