6.6 Patient replacement

Patients who discontinue trial product prematurely will not be replaced.

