8.1.4 Premature discontinuation of trial product

If a patient prematurely discontinues trial product, the investigator must undertake procedures similar to those for visit 9 (the last treatment in the main part) or visit 16 (the last treatment visit in the extension part) as soon as possible. The follow up visit (visit 17) must be performed 8 weeks (window minus 7 days) after last dose of trial drug.

The primary reason for premature discontinuation of trial product must be specified in the end of treatment form in the eCRF, and final drug accountability must be performed. A treatment discontinuation session must be made in the IWRS.

The patients who permanently prematurely discontinue trial product at Investigator's discretion due to a safety concern after completion of the main part of the trial may have visit 17 scheduled 8 weeks after visit 16. Furthermore additional unscheduled visits will be conducted at least every 8 weeks for safety assessments (see Section [8.4](#) and [8.5.2](#)), PK and PD markers. The patients who permanently prematurely discontinue trial product due to safety concerns may have the safety follow up period extended at Investigator's discretion until the safety concern have been resolved, but no later than Last Patient Last Visit as defined in Milestones (Section [7](#) of the protocol).

Permanent premature discontinuation of treatment with trial product will lead to patient withdrawal from the trial.

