17.3 Primary endpoint

The primary endpoint is the number of bleeding episodes during at least 24 weeks from treatment onset. All treated bleeding episodes will be considered for this endpoint, including bleeding episodes recorded as post-surgical or caused by surgery or other medical for dental procedures.

The primary endpoint will be estimated using negative binomial regression with log of exposure time (the included observational period of the main part) as offset, providing an actual estimate of the ABR as well as a corresponding 95% confidence interval. The offset for first CPoC criterion is the log of the individual exposure time at the last dose level reached at the time of analysis excluding the 2 weeks run-in period for subjects on 0.15 mg/kg. The offset for the second criterion is the log of the individual exposure time in the main part.

This analysis has the underlying assumption that the missing data mechanism is “missing at random”, i.e. MAR. Under this assumption, the statistical behaviour of the missing data (given the observed responses and the mean value structure) is assumed to be the same as for the observed data. The endpoint will be estimated based on the full analysis set (FAS) and only data collected

Protocol
 Trial ID:NN7415-4255
 UTN:U1111-1179-3872
 EudraCT no.:2016-000614-29

~~CONFIDENTIAL~~

Date: 28 August 2018
 Version: 5.0
 Status: Final
 Page: 105 of 127

Novo Nordisk

prior to discontinuation of trial product or initiation of alternative treatment options will be used to draw inference.

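### Section 6.4 item 9 leaves out the limit that 5.3.1 puts on the mandatory stop at 0.25 mg/kg, so read literally it is met on day 1 by most patients just escalated to that dose

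*Protocol*

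**What the plan says.** Section 5.3.1 sets out the procedure at 0.25 mg/kg. When a spontaneous bleed occurs, the investigator checks whether at least 3 have occurred within the preceding 12 weeks, "counting only the new sBEs from the beginning of the 0,25mg/kg treatment period". If so, "then the patient must be discontinued from treatment due to lack of efficacy", and the reader is sent to 6.4.

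Section 6.4 lists the conditions under which trial product must be stopped. Item 9 reads "Lack of efficacy defined as ≥ 3 treated sBEs within the previous 12 weeks in patients being treated with the highest dose level" (0.25 mg/kg). It says nothing about when the counted bleeds must have started, and 6.4 does not refer back to 5.3.1; it refers only to 8.1.4.

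Escalation from 0.20 to 0.25 mg/kg requires at least 3 spontaneous, treated bleeds within 12 weeks, counted from the start of 0.20 mg/kg (5.3.1). It takes place at the next scheduled visit, or earlier at an unscheduled one. Visits are 4 weeks apart in the main part. In the extension 5.3.1 allows for a longer wait: "Since the patient may have to wait up to 8 weeks for the next scheduled visit (in the extension part").

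A stop is final. Under 8.1.4, "Permanent premature discontinuation of treatment with trial product will lead to patient withdrawal from the trial", and under 6.6, "Patients who discontinue trial product prematurely will not be replaced".

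**The concern.** Two mandatory rules govern the same patients and count different bleeds. Item 9 requires the patient to be on 0.25 mg/kg; it does not require the bleeds to have occurred there. Because the last escalation step is granted for the same number of bleeds in the same length of window, the history that admits a patient to 0.25 mg/kg is normally enough to stop him under item 9.

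What is at stake is mainly the individual patient, who would lose the last dose step before it had been tried. Two sites could also treat identical patients differently, one keeping the patient under 5.3.1 and the other withdrawing him under 6.4. Section 19.1 rules out waivers, so a site that notices the conflict has no clean way to set item 9 aside. For the analysis, an unneeded stop shortens exposure at 0.25 mg/kg, for which 17.5 wants a separate rate estimate, and adds a discontinued patient to the tipping-point analysis in 17.4.

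**Working it through.** The protocol gives no figure on this point, so there is none to reproduce. The check has three steps.

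**1. The two rules on the same patient.** Days are counted from the start of 0.20 mg/kg, and 12 weeks = 84 days.

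- Bleeds on days 10, 30 and 50, escalation at a visit on day 56. The window reaches back to 56 − 84 = day −28, so all three bleeds count. Item 9 is met on day 1 of 0.25 mg/kg. The 5.3.1 count is 0.
- Bleeds on days 0, 40 and 83 (span 83 days, so the trigger is met), escalation on day 111 after a 28-day wait. The window reaches back to 111 − 84 = day 27, so two bleeds count and item 9 is not met on day 1. A single new bleed on day 124 has a window back to 124 − 84 = day 40, so the bleeds on days 40, 83 and 124 count and item 9 is met. The 5.3.1 count is 1.

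So item 9 is met on day 1 for most newly escalated patients but not all. A patient escalated on the trigger day itself always meets it.

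**2. How often.** The protocol does not give the spontaneous bleed rate on 0.20 mg/kg among patients who escalate, so a range of 4 to 30 per year is assumed. The upper end matches the on-demand level of about 30 cited in section 17. Bleeds were simulated as a Poisson process until 3 fell within 84 days, with escalation at the next visit and further bleeds accruing during the wait. The bleeds in the 84 days before escalation were then counted. Share meeting item 9 as worded on day 1:

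| sBEs per year on 0.20 mg/kg | 4 | 6 | 9 | 12 | 20 | 30 |
|---|---|---|---|---|---|---|
| 4-weekly visits | 79% | 83% | 89% | 93% | 98% | >99% |
| 8-weekly visits | 64% | 71% | 79% | 86% | 96% | 99% |
| Escalated on trigger day | 100% | 100% | 100% | 100% | 100% | 100% |
| Under the 5.3.1 count | 0% | 0% | 0% | 0% | 0% | 0% |

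A separately programmed simulation gave 79–81% at 4 per year and 93% at 12 per year with 4-weekly visits, and 64–66% and 86–87% with 8-weekly visits. With assumed rates of 2 to 12 per year on 0.25 mg/kg, the share meeting item 9 on day 1 or at the first new bleed was 85–100% (4-weekly) and 70–100% (8-weekly).

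**3. How many patients in the main part.** From the protocol: 33 dosed patients (6.1), an ABR of 5.4 over about 8 months for the escalation regimen, and over-dispersion 6 (17.1). Assumed: 70% of bleeds spontaneous, all bleeds treated, follow-up uniform on 24 to 45 weeks (mean 34.5 weeks, about 8 months), and gamma-distributed patient rates. The gamma shape is the 24-week mean divided by (over-dispersion − 1): 5.4 × 24/52 = 2.49, and 2.49/5 = 0.50. The investigator's safety review before escalation is not modelled, so the numbers reaching 0.25 mg/kg are upper values.

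| | Bleed rate unchanged by dose | Rate halves per dose step |
|---|---|---|
| Patients reaching 0.25 mg/kg | 3.0 | 1.5 |
| Share meeting item 9 on day 1 | 94% | 88% |
| Efficacy stops under 5.3.1 | 1.5 | 0.2 |
| Efficacy stops under item 9 as worded | 2.9 | 1.3 |
| Extra stops | 2.9 − 1.5 = 1.4 | 1.3 − 0.2 = 1.1 |
| End-dose ABR, 5.3.1 / item 9 | 2.97 / 2.55 | 2.56 / 2.49 |

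Varying the ABR (4 to 6), over-dispersion (3 or 6) and spontaneous share (50% to 90%) moves the number reaching 0.25 mg/kg between 1.7 and 4.4 (0.7 and 2.4 with halving). The day-1 share stays at 92–95% (83–91%).

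**The case against.** The strongest reply is that the protocol already resolves this. Section 5.3.1 gives the full procedure: what prompts the check, which bleeds count, and the consequence. A site has just used that section to escalate the patient. Lack of efficacy at the highest dose is most naturally read as failure on that dose, and a rule that stopped patients on the day they were escalated would make no sense. Both wordings entered together in amendment 1, so they were surely meant as one rule.

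Most of this stands. The 5.3.1 count is evidently the intended one, and a careful site would follow it. But 6.4 is the formal list of mandatory stops, its wording does not carry the limit, and nothing in it points back to 5.3.1. Amendment 1 was written to clarify the discontinuation criteria and left two different counts. Nor is the point out of date: escalation continues through the extension, for up to 126 weeks of treatment.

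Three stronger readings are tempting and should not be drawn.

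- A reader might infer that the end-dose rate could also rise, because the trigger bleeds would stay in the analysis if the patient were stopped before any 0.25 mg/kg dose. Item 9 applies only to patients being treated with 0.25 mg/kg, so that case does not meet it. Once a dose has been taken, 17.3 uses the "individual exposure time at the last dose level reached at the time of analysis" and the bleeds on 0.20 mg/kg drop out.
- A reader might infer that the primary result or the power is compromised. The end-dose rates in the working all lie far below 12, and the power calculation in 17.1 does not use the stop rule.
- A reader might take footnote p of Table 2-2 ("if he experiences ≥ 3 spontaneous bleeding episodes within the preceding 12 weeks of treatment with concizumab") as a further fault of the same kind. That footnote concerns escalation, not stopping, and the visit sections already send the investigator to 5.3.1.

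**Conclusion.** The inconsistency is real and lies in current text. Item 9 of 6.4 is wrong as written; the design in 5.3.1 is not in question. That most newly escalated patients meet item 9 on day 1 holds throughout the range examined, with 64% the lowest share (4 bleeds per year, 8-weekly visits). The bleed rates are assumptions, and the percentages describe what happens if a site applies item 9 to the letter, not what sites would be expected to do.

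The practical weight is moderate to small. About one extra patient would be stopped in the main part under the assumed inputs. For that patient the consequence is irreversible, which is why a mandatory stop rule should be corrected even when the intent can be worked out. Sample size, power and the proof-of-concept conclusion are unaffected.

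**What to change.** Reword 6.4 item 9 so that it requires at least 3 treated sBEs within the previous 12 weeks, counting only new sBEs from the start of 0.25 mg/kg treatment (see Section 5.3.1). With that limit, no patient meets the criterion at escalation or at his first new bleed; three new bleeds within 12 weeks on 0.25 mg/kg are needed, as 5.3.1 intends. The cost is one clause in the next amendment, with no new data, visits or analyses. Until then, a short clarification to sites that 5.3.1 defines the count would serve.
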